### **3. Intake Visit with Study Physician**

- a. This visit may occur in-person or via telehealth, at the Study Physician's discretion.
- b. If this visit occurs in-person:
  - i. Conduct physical exam. Documentation will be in EMR.
  - ii. Assess and confirm/infer ADHD diagnosis.
    - 1. For participants without a formal diagnosis of ADHD (e.g. documentation of ADHD in participant's electronic medical record), responses to questionnaires from parent and teacher will be sought prior to diagnosis. During the COVID-19 pandemic, teacher response are will not always available. In the event that teacher responses are not

available, the Study Physician may infer a diagnosis with the information that is available to the Study Physician, (e.g. school reports, previous teacher's feedback) at their clinical discretion. Follow-up for a formal diagnosis is at the discretion of the Study Physician and is dependent on the pandemic situation and the available tools for diagnosis available while the participant is active in the study.

2. For participants with a pre-existing diagnosis of ADHD, data from participant EHRs may be used to support confirmation of a diagnosis. EHRs from clinics outside of Children's Mercy Hospital may be requested in the course of clinical practice.
  - iii. Assess and confirm diagnosis of other comorbidities.
  - iv. Assess and confirm appropriateness of atomoxetine therapy for participant.
  - v. Assess for adverse events. Document in Adverse Events log.
  - vi. Complete Clinical Global Impression (CGI).
- c. If this visit occurs via telehealth, the physical exam will be omitted.
- d. This visit may occur before enrollment if participant is referred from a Study Physician. This visit can occur within 6 weeks enrollment.
- e. If Children's Mercy Hospital develops procedures for drive-up collection of vital signs (e.g. heart rate, blood pressure), the Study Physician may ask the participant to use this service to supplement their evaluation.

#### 4. Research Visit 2

##### *Prior to Visit*

- a. Obtain *CYP2D6* genotyping results for participant to calculate *CYP2D6* activity score and determine a *CYP2D6* predicted phenotype.
- b. Determine whether the First Dose Pharmacokinetic Study of atomoxetine for participant will be Study Design 1 or Study Design 2.
- c. Determine an atomoxetine dose using participant *CYP2D6* predicted phenotype, height, weight, obesity status, and gender obtained from Research Visit 1. This dose will be simulated to target a plasma  $C_{max,ss}$  of 400 ng/mL. This will be determined using the iGO-PK model (see section 5.1 above) .
- d. Obtain a signed and dated prescription from a Study Physician for a dose of atomoxetine that is expected to result in a plasma  $C_{max,ss}$  of 400 ng/mL.
- e. Optional: Obtain a signed and dated prescription for topical lidocaine (either J-tip or cream) to alleviate pain with needlestick for participant.

- f. Submit signed and dated prescription to Children's Mercy Hospital Investigation Drug Services (IDS) pharmacy.
- g. Confirm placement in Study Design 1 or Study Design 2.
- h. Contact participant and participant's family prior to the visit to:
  - a. Remind them of their scheduled Research Visit 2.
  - b. Inform as to which Study Design the participant will be under for Research Visit 2 and all remaining research visits.
  - c. Instruct participant to begin fasting at midnight prior to coming in for Research Visit 2. Water is permissible while fasting.
  - d. The research team will ensure that the participant and their family are aware of the safety measures at Children's Mercy Hospital to prevent transmission of the SARS-CoV-2 virus. These resources and information to be shared will be detailed on the Children's Mercy Hospital homepage and any PCRU guidance in response to COVID-19.

*On Day of Visit*

- a. Confirm participant's willingness to continue in the research study.
- b. Obtain medication history and concomitant medications. Add to Concomitant and Prior Medications Log.
- c. Measure vital signs: height, weight, blood pressure, heart rate, respiration rate, and temperature.
- d. Perform physical exam.
- e. Place indwelling venous catheter to obtain blood samples for safety labs and for atomoxetine pharmacokinetic and pharmacodynamic analysis.
- f. Collect blood samples for the following safety laboratory tests (to be processed immediately at Children's Mercy Hospital): CBC with differential, basic metabolic panel, and liver function test.
  - i. These tests may be omitted if these data were collected in the week prior, at the discretion of the study coordinator, the physician performing the physical exam, or any person designated in the delegation of authority log.
- g. Collect urine for urinalysis with microbiology.
- h. Perform urinary pregnancy test on female subjects.
- i. Collect baseline urine sample (~10 mL) for predose urine sample and CYP2D6 biomarker analysis.
- j. Confirm prior to dosing that participant is:
  - i. Healthy enough to continue Research Visit 2 (sign off on safety labs and physical exam sheet by physician).
  - ii. Not pregnant, females only (urine pregnancy test).
- k. Place two sweat patches on the participants back. The sweat patch is 15.4 cm^2 in size and consists of a cellulose blotter paper collection pad

(PharmChek®, PharmaChem Laboratories, Menlo Park, CA). Prior to patch placement, clean the area of skin to which the patch will be applied with rubbing alcohol.

- i. Collect pre-dose blood, blood pressure, and heart rate prior to dosing medication.
- m. Administer dose of atomoxetine according to prescription.
- n. Collect 3 mL of blood, blood pressure, and heart rate at the following time points after dose administration:
  - i. Timeframe:
    - i. Study Design 1: 0.5, 0.75, 1, 1.5, 2, 3, 4, 6, 8, 10, 12, 16, 20, 24, 48, and 72 hours.
    - ii. Study Design 2: 0.5, 0.75, 1, 1.5, 2, 3, 4, 6, 8, 10, and 12 hours.
    - iii. A window of  $\pm$  5 minutes is acceptable for blood draws at time points 0.5 – 2 hours.
    - iv. A window of  $\pm$  15 minutes is acceptable for blood draws at all other time points.
  - ii. Collection Instructions: 2 mL of blood will be collected in a EDTA tube and 1 mL of blood will be collected in a serum gel separator tube.
  - iii. Processing: Within an hour of collecting sample, plasma and serum will be separated by centrifugation at 4°C (1000 – 2000 g x 10 min), aspirated manually, and transferred to polypropylene cryovials for storage at -70°C until analysis.
- o. Collect and pool urine starting after dose administration.
  - i. Study Design 1: collect all urine for the first 24 hours in the PCRU. Discharge participant with urine jug at 24 hour and 48 hour time point and instruct participants to return urine jug 24 hours later to PCRU. Record volume of urine excreted for the intervals of 0-24 hrs, 24-48 hrs, and 48-72 hours post drug administration. Collect a ~10 mL sample from each urine interval. NB: The study team will instruct the participant that every attempt should be made to collect all urine, however the team recognizes that collecting urine while at school or at work may not be feasible.
  - ii. Study Design 2: collect all urine 12 hours post drug administration. Record the volume of urine excreted. Collect a ~10 mL sample.
- p. Collect ~ 2 mL of saliva. Instruct participant not to eat or drink for 30 minutes prior to beginning to spit.
- q. Remove sweat patches
  - i. For Study Design 1, remove one sweat patch 12 and 24 hours post drug administration. Place sweat patch in labeled ziplock bag for storage at -70°C until analysis.

- ii.* For Study Design 2, remove one sweat patch 8 and 12 hours post drug administration. Place sweat patch in labeled ziplock bag for storage at -70°C until analysis.
- r. The research team will ask the participant to fast for 2 hours after drug administration. After this 2-hour mark, the participant is free to eat and drink as desired. Document all meal times and content. Collect food receipts when available. The following are scenarios where the research team may deviate from fasting for 2 hours post-administration:
  - i.* A participant may request to take atomoxetine with a small amount of soft food (e.g., pudding, applesauce, etc.) to aid with capsule swallowing. Document the food and approximate volume the participant used to aid with capsule swallowing (e.g., participant took capsule with ~1 teaspoon of chocolate pudding).
  - ii.* If participant reports GI upset, a small snack may be given to alleviate symptoms, even in the event that the fasting time has not been completed. Document GI upset as an adverse event in the adverse events log. If snack is given, document the snack time and content.
- s. Perform assessment of attention tasks (Pupillometry during Posner's Cuing Task). Further details can be found in Appendix H.
- t. Perform Tanner Staging exam. This procedure is optional according to participant preference. The participant does not need to have Tanner Staging if this was performed previously within 4 weeks prior of Research Visit 2 or if the participant has already reached maximum stage in a prior Tanner staging exam.
- u. Dispense medication to participant and discuss instructions on atomoxetine prescription and for medication calendar.
- v. Assess for adverse events. Document in Adverse Events log.
- w. Add compensation to participant's Greenphire account.

## 5. Research Visit 3

### *Prior to Visit*

- a. Optional: Obtain a signed and dated prescription from a Study Physician for topical lidocaine (either J-tip or cream) to alleviate pain with needlestick for participant.
- b. Submit signed and dated prescription to Children's Mercy Hospital Investigation Drug Services (IDS) pharmacy.
- c. Confirm participation in Study Design 1, Study Design 2, or need to switch to Study Design 3.
- d. If participant will be changing to Study Design 3, discuss with participant and/or family changes from Study Design 2.

- e. Contact participant and participant's family between 8-10 days prior to Research Visit 3 to remind participant to take all prescribed doses the week prior to Research Visit 3.
- f. Contact participant and participant's family 1 -2 days prior to the visit to:
  - i. Remind them of their scheduled visit.
  - ii. Ensure that participant has been compliant on medication for 1 week prior to scheduled Research Visit 3.
    - i. If the participant has not been compliant, the visit will need to rescheduled.
  - iii. Instruct participant to begin fasting at midnight prior to the visit. Water is permissible while fasting.
  - iv. Remind participant to bring their home atomoxetine medication to the PCRU, but to not take the medication in the morning.
  - v. Remind participant to bring U54 Study Booklet, which contains the participant's medication calendar.
  - vi. If participant has been switched to evening dosing of ATX, schedule Research Visit 3 to mirror how the participant typically takes their medication. (i.e. if the participant takes their medication in the evening, the beginning of their pharmacokinetic study should also be in the evening).
  - vii. The research team will ensure that the participant and their family are aware of the safety measures at Children's Mercy Hospital to prevent transmission of the SARS-CoV-2 virus. These resources and information to be shared will be detailed on the Children's Mercy Hospital homepage and any PCRU guidance in response to COVID-19.

*On Day of Visit*

- a. Confirm participant's willingness to continue in the research study.
- b. Obtain medication history and concomitant medications. Add to Concomitant and Prior Medications Log.
- c. Verify medication calendar with remaining capsules count.
- d. Make copies of pages in medication calendar.
- e. Measure vital signs: height, weight, blood pressure, heart rate, respiration rate, and temperature.
- f. Perform physical exam.
- g. Place indwelling venous catheter to obtain blood samples for safety labs and for atomoxetine pharmacokinetic and pharmacodynamic analysis.
- h. Collect blood samples for the following safety laboratory tests (to be processed immediately at Children's Mercy Hospital): CBC with

differential, basic metabolic panel, and liver function test. These tests may be omitted if these data were collected in the week prior, at the discretion of the study coordinator, the physician performing the physical exam or any person designated in the delegation of authority log.

- i. Collect urine for urinalysis with microbiology.
- j. Perform urinary pregnancy test on female subjects 10 years of age or older.
- k. Collect baseline urine sample (~10 mL) for predose urine sample and CYP2D6 biomarker analysis.
- l. Confirm prior to dosing that participant is:
  - i. Healthy enough to continue Research Visit 3 (sign off on safety labs and physical exam sheet by physician).
  - ii. Not pregnant, females only (urine pregnancy test).
  - iii. Has been compliant with medication (medication calendar check). If the participant has not been compliant, the visit will need to rescheduled.
- m. Place two sweat patches on the participant's back. The sweat patch is 15.4 cm^2 in size and consists of a cellulose blotter paper collection pad (PharmChek®, PharmaChem Laboratories, Menlo Park, CA). Prior to patch placement, clean the area of skin to which the patch will be applied with rubbing alcohol.
- n. Collect pre-dose blood, blood pressure, and heart rate prior to dosing medication.
- o. Administer dose of atomoxetine according to prescription.
- p. Collect 3 mL of blood, blood pressure, and heart rate at the following time points after dose administration:
  - i. Timeframe:
    - i. Study Design 1: 0.5, 0.75, 1, 1.5, 2, 3, 4, 6, 8, 10, 12, 16, 20, and 24 hours.
    - ii. Study Design 2: 0.5, 0.75, 1, 1.5, 2, 3, 4, 6, 8, 10, 12 hours.
    - iii. Study Design 3:
      - 1. Following first dose: Collect at 0.5, 0.75, 1, 1.5, 2, 3, 4, 6, 8, 10, and 12 hours as applicable following first dose and will continue only until the second dose is given.
      - 2. Second dose will be given at the same time increment between when participant routinely takes their first and second dose ± 5 minutes (eg. If 6 hours are between routine dosing for participant, the second study dose will be given 6 hours ± 5 minutes after the first dose).

3. Collect predose blood, blood pressure, heart rate prior to dosing 2nd dose
4. Once the second dose is given, continued blood draws, blood pressure, and heart rate collection based on the timing of the *first* dose will stop.
5. Timing of blood, blood pressure, and heart rate will now be timed according to *second* dose only.
6. Timing of collections will restart, with timepoints 0.5, 0.75, 1, 1.5, 2, 3, 4, 6, 8, 12, and 16 hours after the second dose.
  - iv. A window of  $\pm$  5 minutes is acceptable for blood draws at time points 0.5 – 2 hours.
  - v. A window of  $\pm$  15 minutes is acceptable for blood draws at all other time points.
- ii. Collection Instructions: 2 mL of blood will be collected in an EDTA tube and 1 mL of blood will be collected in a serum gel separator tube.
- iii. Processing: Within an hour of collecting sample, plasma and serum will be separated by centrifugation at 4°C (1000 – 2000 g x 10 min), aspirated manually, and transferred to polypropylene cryovials for storage at -70°C until analysis.

q. Collect and pool urine starting after dose administration.

- i. Study Design 1: collect all urine for the first 24 hours in the PCRU. Record the volume of urine excreted. Collect a ~10 mL sample and store in 15 mL polypropylene falcon tubes for storage at -70°C until analysis.
- ii. Study Design 2: collect all urine 12 hours post drug administration. Record the volume of urine excreted. Collect a ~10 mL sample and store in 15 mL polypropylene falcon tubes for storage at -70°C until analysis.
- iii. Study Design 3: collect all urine starting after the first dose and continuing through 16 hours post second dose administration. Record the volume of urine excreted. Collect a ~10 mL sample and store in 15 mL polypropylene falcon tubes for storage at -70°C until analysis.

r. Collect ~ 2 mL of saliva. Instruct participant not to eat or drink for 30 minutes prior to beginning to spit.

s. Remove sweat patches

- i. For Study Design 1, remove one sweat patch 12 and 24 hours post drug administration. Place sweat patch in labeled ziplock bag for storage at -70°C until analysis.

- ii.* For Study Design 2, remove one sweat patch 8 and 12 hours post drug administration. Place sweat patch in labeled ziplock bag for storage at -70°C until analysis.
    - iii.* For Study Design 3, remove one sweat patch 8 and 16 hours post second drug dose administration. Place sweat patch in labeled ziplock bag for storage at -70°C until analysis.
  - t.* The research team will ask the participant to fast for 2 hours after drug administration. After this 2 hour mark, the participant is free to eat and drink as desired. Document all meal times and content. Collect food receipts when available. The following are scenarios where the research team may deviate from fasting for 2 hours post-administration
    - i.* A participant may request to take atomoxetine with a small amount of soft food (e.g., pudding, applesauce, etc.) to aid with capsule swallowing. Document the food and approximate volume the participant used to aid with capsule swallowing (e.g., participant took capsule with ~1 teaspoon of chocolate pudding).
    - ii.* If participant reports GI upset, a small snack may be given to alleviate symptoms, even in the event that the fasting time has not been completed. Document GI upset as an adverse event in the adverse events log. If snack is given, document the snack time and content
    - iii.* Fasting will not be required for participants taking medication in the evening who are participating in an overnight pharmacokinetic study. The research team does not believe it is feasible to expect a child to fast for 8-12 hours while awake.
    - iv.* If participant is assigned Study Design 3, fasting prior to and/or after the second dose of medication will not be required. The research team does not believe it is feasible to expect a child to fast prior to both the first dose and second dose.
    - u.* Perform assessment of attention tasks (Pupillometry during Posner's Cuing Task). Further details can be found in Appendix H.
    - v.* Perform Tanner Staging. This procedure is optional according to participant preference. The participant does not need to have Tanner Staging if this was performed previously within 4 weeks prior of Research Visit 3 or if the participant has already reached maximum stage in a prior Tanner staging exam.
    - w.* Assess for adverse events. Document in Adverse Events log.
    - x.* Add compensation to participant's Greenphire account.

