#### *iGO-PK Model*

This method was developed using data generated from a previous ATX single-dose PK study conducted at Children's Mercy Hospital (Brown et al., 2016). This model stratifies participants into two distinct populations: individuals who are CYP2D6 PM and those who non-PMs, i.e. IM, EM1, EM2, and UM (read above for more details on *CYP2D6* genotype and phenotype prediction). With the new changes to *CYP2D6* genotype-to-

phenotype interpretation and study design, the only major change is that children with two reduced function alleles will be modeled as an IM. Analysis of the previous PK study found that in non-PM participants, the dose-exposure relationship was best described using a two-compartment model with first order absorption and first order clearance. In PM participants, dose-exposure was best described using a one compartment model with first order absorption, first order clearance, and a secondary peaking component. Additionally, lean body weight (LBW) and obesity status (positive or negative) variables were found to significantly impact variability in ATX exposure in both models.

Retrograde extrapolation of an initial dose of ATX for PK Study 1 will be determined by setting the desired  $C_{max}$  goal at steady-state ( $C_{max,ss}$ ) to 400 ng/mL, and incorporating patient specific parameters CYP2D6 AS, LBW, and obesity status. The actual dose dispensed will be as close as possible to the model generated dose, given the available atomoxetine capsule formulations. Additionally, we will also consider the most convenient combination of capsules for a child to take and how a prescriber would dose this medication in a naturalistic setting. During the course of the study, we will also be monitoring clinical response and toxicity. The exposure ( $C_{max,ss}$ ) may be titrated down to below 400 ng/mL to reduce toxicity or up to 800 ng/mL to increase response as tolerated.

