$C_{max}$	Peak plasma concentration determined from the observed data
$T_{max}$	Time to observed maximum drug concentration
$AUC_{0-\tau}$	Area under the plasma concentration versus time curve, determined by log-linear trapezoidal estimation, to the 12 or 24 hour time point (depending on CYP2D6 AS designated study design).
$AUC_{0-\infty}$	Area under the concentration versus time curve to infinity, determined by log-linear trapezoidal estimation $AUC_{0-\tau} + C_{\tau}/k$ Where $k$ is the elimination rate constant defined as the negative slope following maximum concentration determined by least squares regression from terminal phase data.
$T_{1/2}$	Terminal half-life determined by quotient $0.693/k$
$CL/F$	Oral clearance determined by quotient dose/ $AUC_{0-\infty}$
$Vd/F$	Terminal phase volume of distribution determined by Dose/ $k \cdot AUC_{0-\infty}$

fm	Fraction of drug metabolized through different pathways of biotransformation
----	--

The following PK parameters will be derived by non-compartmental analysis from plasma concentration data following chronic dosing to steady-state of study drug:

$C_{max,ss}$	Peak plasma concentration determined from the observed data at steady-state
$T_{max, ss}$	Time to observed maximum drug concentration at steady-state
$AUC_{0-\tau,ss}$	Area under the plasma concentration versus time curve, determined by log-linear trapezoidal estimation, to the 12 or 24 hour time point (depending on CYP2D6 AS designated study design).
$T_{1/2}$	Terminal half-life determined by quotient $0.693/k$
$CL/F_{ss}$	Oral clearance determined by quotient dose/ $AUC_{0-\infty}$
$Vd/F_{ss}$	Terminal phase volume of distribution determined by Dose/ $k \cdot AUC_{0-\infty}$

iGO-PK Model Update: The current iGO-PK Model (Version 1.0) uses ATX pharmacokinetic data from 24 pediatric participants (Brown et al., 2016). Since the building of Version 1.0, more ATX pharmacokinetic data has been collected from studies conducted at Children's Mercy Hospital (IRB# 16010069) and this current study. The data will be used to update and refine the iGO-PK model when it has been determined that sufficient new data has been collected. This determination will be made by the Principal Investigators and other Co-Investigators.

Pharmacodynamics:

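### In Study Design 1 the steady-state half-life and Vd/F come from 24 h profiles although the same child has a 72 h first-dose profile; pooling the visits and correcting the AUC term is a minor, cheap improvement.

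*Combined protocol and SAP*

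**What the plan says.** Section 11.2, Research Visit 2, item n gives the first-dose sampling as "Study Design 1: 0.5, 0.75, 1, 1.5, 2, 3, 4, 6, 8, 10, 12, 16, 20, 24, 48, and 72 hours". For Research Visits 3 and 4 (item p in each) it is "Study Design 1: 0.5, 0.75, 1, 1.5, 2, 3, 4, 6, 8, 10, 12, 16, 20, and 24 hours". Figure 5 in Section 11.1 shows the same visit lengths: 72 h, then 24 h and 24 h.

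Section 20.1 (Pharmacokinetics) has a second parameter table, derived non-compartmentally from "plasma concentration data following chronic dosing to steady-state of study drug". It includes a half-life, "Terminal half-life determined by quotient" 0.693/k. It also defines CL/F at steady state as dose over AUC0-∞, and Vd/F at steady state as dose over k times AUC0-∞. The only AUC listed in that table is AUC0-tau,ss. The slope k is defined once, in the single-dose table: "negative slope following maximum concentration determined by least squares regression from terminal phase data".

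No minimum span in half-lives and no precision limit for k is stated, and nothing says that the RV2 slope may be used at later visits. The fallback in Section 20.1 depends on the number of post-peak points, not on how much decline they cover.

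Section 5.1 assigns to Study Design 1 every activity score below 1 and children with two reduced-function alleles, so it is not confined to poor metabolisers. It describes the poor-metaboliser profile as one compartment with "first order absorption, first order clearance, and a secondary peaking component".

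**The concern.** A terminal slope is well determined only when the fitted points cover enough decline. The 72 h RV2 profile supplies that for slow eliminators, but RV3 and RV4 stop at 24 h. The steady-state table asks for the same slope-based quantities from the shorter profile, and a count of post-peak points would not flag the problem.

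Two reported parameters are at stake, T1/2 and Vd/F at steady state, in the slower children of Study Design 1. Set beside the RV2 values for the same child, they could differ because of the sampling window alone. The AUC0-∞ term raises a separate question. At steady state, extrapolating to infinity counts drug left from earlier doses, so dividing a single dose by that area understates clearance.

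**Working it through.** **Inputs from the documents.** RV3/RV4 times to 24 h and RV2 times to 72 h (Section 11.2); k as a terminal regression slope, T1/2 = 0.693/k, and the AUC0-∞ definitions (Section 20.1); once-daily dosing as usual (Section 11.1). The plan states no half-life and no precision for k, so there is no figure of its own to reproduce.

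**Assumptions.** One compartment, ka = 1/h, 24 h interval, lognormal residual error with CV 10% or 15% (sigma = √ln(1 + CV²) = 0.0998 or 0.149), and half-lives from 5 to 24 h. The start of the terminal phase is not specified, so three windows are shown.

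**Step 1: span.** Half-lives covered = (24 − start)/T1/2. From 12 h: 1.2 at T1/2 = 10 h, 1.0 at 12 h, 0.6 at 20 h. From 8 h: 1.6 at 10 h, 1.0 at 16 h, 0.8 at 20 h. The span is one half-life or less only if T1/2 is at least 12 h (fit from 12 h) or 16 h (fit from 8 h). RV2 from 12 to 72 h covers 60/20 = 3.0 half-lives at 20 h.

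**Step 2: precision of k.** Relative SE = sigma/(k·√Sxx), where Sxx is the sum of squared deviations of the sampling times. The half-life misses by more than 30% if the estimate of k is below k/1.3 or above k/0.7. With SE the relative SE, that probability is Φ(−0.231/SE) + Φ(−0.429/SE). At T1/2 = 20 h, k = 0.0347/h:

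| Fit | Sxx (h²) | Relative SE, CV 10% / 15% | Miss by >30% |
|---|---|---|---|
| RV3/RV4, 6–24 h | 259 | 18% / 27% | 11–25% |
| RV3/RV4, 8–24 h | 190 | 21% / 31% | 15–31% |
| RV3/RV4, 12–24 h | 80 | 32% / 48% | 33–50% |
| RV2, 24, 48, 72 h | 1152 | 8% / 13% | under 1% to about 4% |
| RV2, 12–72 h | 2720 | 6% / 8% | under 1% |

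Example, 12–24 h at CV 15%: 0.149/(0.0347 × √80) = 0.48.

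Simulated profiles agree. At 20 h and CV 15%, the 5th–95th percentile range of T1/2 is 13.2–41.4 h (8–24 h fit) or 11.1–90.3 h (12–24 h fit), against 17.6–23.2 h from RV2 at 12–72 h.

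At T1/2 = 10 h, k doubles and every relative SE halves: 9–13%, 10–16% and 16–24% for the three 24 h windows, with 0.5–4%, 1–7% and 8–21% missing by more than 30%.

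**Step 3: secondary peak (illustrative).** The plan gives no size or timing. A noise-free peak of 10–20% at 10 or 12 h moves a true 20 h half-life to 14.1–18.2 h on the RV3 times (fits from 8 or 12 h), but only to 19.2–19.7 h on the RV2 times.

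**Step 4: AUC0-∞ at steady state.** For once-daily dosing, true CL/F = Dose/AUC0-tau,ss. Extrapolating the steady-state profile adds C(24)/k, so with E = e^(−24k):

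Dose/AUC0-∞ ÷ true CL/F = 1/[1 + (ka/(ka − k))·E/(1 − E)]

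- T1/2 = 10 h: E = 0.1895; 1/(1 + 1.0745 × 0.2338) = 0.80.
- T1/2 = 20 h: E = 0.4353; 1/(1 + 1.0359 × 0.7708) = 0.56.

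Vd/F is low by the same factor, even when k is exact.

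**The case against.** The strongest reply is that the 24 h stop is deliberate and coherent. With once-daily dosing, 24 h is the whole interval, which is what Cmax,ss and AUC0-tau,ss need. That stands: the sampling schedule is not at fault, only what the steady-state table asks of it.

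The size also depends on choices the plan leaves open. Under a one-compartment model a fit could start at 6 h, which roughly halves the imprecision of the 12–24 h fit. Children in Study Design 1 with a half-life near 10 h would mostly be served well enough. Both points stand, and they are why the result is given as a range.

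Section 20.1 also plans weighted nonlinear fitting and inspects coefficients of variation and parameter correlations, which could expose a poor slope. This helps only in part, because the tabulated parameters are labelled non-compartmental and no action follows from a poor value.

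Finally, no hypothesis in Section 2.2 and no sample-size calculation in Section 20.2 uses steady-state T1/2 or Vd/F, and no comparison of half-lives between visits is planned. That stands and sets the severity. Section 20.1 does relate pupillometry to Cmax and AUC0-∞, but it names no visit and uses neither parameter.

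**Conclusion.** The point holds as a minor one. If the half-life is about 12–16 h or more, a slope from a single RV3 or RV4 profile is imprecise: at 20 h, relative SE 18–48% and 11–50% of half-lives off by more than 30%, against 6–13% and at most about 4% with the RV2 times. A secondary peak may add bias. If AUC0-∞ is extrapolated from the steady-state profile, the definitions make CL/F and Vd/F low by a factor of 0.80 (10 h) to 0.56 (20 h). All of this rests on the assumed half-lives, CV, ka and one-compartment form.

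A reader might infer more, and the documents do not support it:

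- That every child in Study Design 1 has about one half-life or less of decline, or that the estimates will be mostly noise. No half-life is given, and the group includes intermediate metabolisers.
- That only slow metabolisers are affected. Study Design 2 stops at 12 h; with an assumed 6 h half-life and a 6–12 h fit (Sxx = 20), the relative SE is 19–29%.
- That the error passes into the iGO-PK update or the primary analyses. The plan does not say that the update uses these tabulated parameters, and the primary hypotheses do not.

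**What to change.** Edit the steady-state table in Section 20.1, for Study Design 1:

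1. Estimate k by a joint fit of RV2, RV3 and RV4 with the dosing record. Alternatively take k from RV2 and label it as the RV2 value, not as an independent steady-state estimate.
2. Report a T1/2 from a single RV3 or RV4 profile only when the terminal points span a pre-stated number of half-lives, for example two.
3. Define CL/F at steady state as Dose/AUC0-tau,ss and Vd/F at steady state as Dose/(k × AUC0-tau,ss), with tau the dosing interval.

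Make the changes together. Borrowing k alone leaves the 0.56–0.80 factor in place. Changing the AUC alone lets the full relative error in k reach Vd/F, whereas under the extrapolated form at 20 h only about 0.56 of it does.

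The table now ties the AUC limit to the study design (12 or 24 h). For Study Design 1 on once-daily dosing, 24 h is already the interval. For Study Design 2 on once-daily dosing the profile covers half of it, so the text should say how the remainder is obtained.

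Cost: SAP wording and a little more modelling, with no new blood draws or visits. Using RV2's k assumes that elimination does not change between first dose and steady state; the joint fit can check this.
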